5.2.1. Analyses for Binary Data

Number and percentage of subjects will be summarized. Line plots of proportions may be provided.

5.2.2. Analyses for Continuous Data

Number, mean, standard deviation, standard error of the mean, median, minimum, and maximum will be presented. Line plots of means and standard errors may be provided.

5.2.3. Analyses for Categorical Data

The frequency and percentage for each category will be presented.

5.2.4. Analyses for Time to Event Data

Time to event endpoints will be summarized using the Kaplan-Meier (KM) method and estimated survival curves will be displayed graphically when appropriate. Graphs will describe the number of patients at risk over time. The median, quartiles, 95% confidence interval (CI) for median and quartiles will be estimated by the KM method.

5.3. Methods to Manage Missing Data

In general, for analyses using descriptive statistics, missing values will not be imputed. In addition, for safety endpoints, missing values will not be imputed. Other methods for handling missing values are discussed below.

5.3.1. Binary Endpoints

For binary endpoints analyzed at each scheduled visit separately, if a subject has no data for a binary endpoint at a scheduled visit, this subject will be classified as a non-responder (NR) for that endpoint at that visit.

5.3.2. Continuous Endpoints

Observed data will be used for all continuous endpoints.

5.3.3. Time to Event Endpoints

For time-to-event endpoints, subjects who complete the study without the event of interest or those who withdraw before experiencing the event of interest will have their event times right censored at the last available measurement time (or visit) used to define whether the subject experienced the associated event (ie, the event of interest is presumed to have occurred beyond this time point).

6. ANALYSES AND SUMMARIES

Due to study termination, only 40% of participants were enrolled. No statistical analysis and comparison will be performed. Only descriptive summary will be performed for selected efficacy and PRO endpoints.

Summary of selected efficacy and PRO endpoints will be based on FAS population. [Section 5.2](#) provides treatment groups for summary.

6.1. Efficacy Endpoints

6.1.1. Percent Change from Baseline in EASI at Days 8, 15, 22, and 29

Descriptive statistics and graph will be provided for observed percent change from baseline in EASI.

6.1.2. Percent Change from Day 29 to Day 43 in EASI

Descriptive statistics will be provided for observed percent change from Day 29 to Day 43 in EASI.

6.1.3. ISGA of Success at Days 8, 15, 22, and 29

Achievement of success in the ISGA (defined as an ISGA score of clear (0) or almost clear (1) with at least a 2-grade improvement from baseline) at Days 8, 15, 22, and 29 will be summarized. Missing data will be classified as non-responder.

6.1.4. ISGA of Clear or Almost Clear at Days 8, 15, 22, and 29

Achievement of ISGA of clear (0) or almost clear (1) at Days 8, 15, 22, and 29 will be summarized. Missing data will be classified as non-responder.

6.1.5. EASI75 at Days 8, 15, 22, and 29

Achievement of EASI75 at Days 8, 15, 22, and 29 will be summarized. Missing data will be classified as non-responder. Graph depicting proportions will be provided.

6.1.6. Time to EASI75

Time to event endpoints will be summarized using the KM method and estimated survival curves will be provided for time to EASI75. The median, quartiles, 95% CI for median and quartiles be estimated by the KM method.

6.1.7. Change from Baseline in %BSA at Days 8, 15, 22, and 29

Descriptive statistics will be provided for observed change from baseline in %BSA.

6.2. PRO Endpoints

6.2.1. Change from Baseline in Weekly Average Peak Pruritus NRS/Scale

For peak pruritus NRS/Scale, weekly average score will be used in the analyses of change from baseline. Observed change from baseline in weekly average peak pruritus NRS/Scale at Days 8 (Week 1 average of Days 2-8), 15 (Week 2 average of Days 9-15), 22 (Week 3 average of Days 16-22), and 29 (Week 4 average of Days 23-29) for subjects ≥ 12 years will be summarized.

6.2.2. Change from Baseline in Weekly Average Patient Reported Itch Severity Scale

Due to the low enrollment, Patient Reported Itch Severity Scale will not be summarized.

6.2.3. Change from Baseline in Weekly Average Observer Reported Itch Severity Scale

Due to the low enrollment, Observer Reported Itch Severity Scale will not be summarized.

6.2.4. ≥ 2 -Point Improvement in Weekly Average Peak Pruritus NRS

Achievement of ≥ 2 -point improvement from baseline in weekly average peak pruritus NRS at Days 8 (Week 1 average of Days 2-8), 15 (Week 2 average of Days 9-15), 22 (Week 3 average of Days 16-22), and 29 (Week 4 average of Days 23-29) will be summarized for subjects ≥ 12 years. Missing data will be classified as non-responder.

6.2.5. ≥ 3 -Point Improvement in Weekly Average Peak Pruritus NRS

Achievement of ≥ 3 -point improvement from baseline in weekly average peak pruritus NRS at Days 8 (Week 1 average of Days 2-8), 15 (Week 2 average of Days 9-15), 22 (Week 3 average of Days 16-22), and 29 (Week 4 average of Days 23-29) will be summarized for subjects ≥ 12 years. Missing data will be classified as non-responder.

6.2.6. Change from Baseline in DLQI at Days 8, 15, 22, and 29

Descriptive statistics will be provided for observed change from baseline in DLQI for subjects ≥ 16 years.

6.2.7. Change from Baseline in CDLQI at Days 8, 15, 22, and 29

Descriptive statistics will be provided for observed change from baseline in CDLQI for subjects 4-15 years.

6.2.8. Change from Baseline in DFI at Days 8, 15, 22, and 29

Descriptive statistics will be provided for observed change from baseline in DFI completed by parent/caregiver of subjects 2-17 years.

CCI

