3. STUDY DESIGN

This is a Phase 3b/4, multicenter, randomized, assessor blinded, vehicle and active (TCS and TCI) controlled study of the efficacy, safety and local tolerability of crisaborole ointment, 2% in pediatric and adult subjects, ages 2 years and older, with mild to moderate AD involving at least 5% treatable %BSA. Treatment will be clinical assessor-blinded for all treatment arms and double-blinded for crisaborole ointment, 2% and vehicle treatment arms.

A total of approximately 600 subjects will be enrolled in the study, of which at least 150 subjects aged 2-6; at least 140 subjects aged 7-11; at least 120 subjects aged 12-17 and up to 90 subjects will be adults. Following the screening period (up to 35 days prior to Baseline/Day 1), eligible subjects will be randomized at the Baseline/Day 1 visit.

Randomization will be stratified by eligibility for TCS or TCI treatment as per national approved labels and eligibility provided in [Section 4](#). Cohort 1 will be for subjects who are eligible for TCS therapy, and Cohort 2 will be for subjects who are not eligible for TCS therapy but eligible for TCI therapy. The investigational product will be applied BID for 28 days to the Treatable BSA identified at Baseline/Day 1. Any new AD on treatment-eligible locations occurring following Baseline/Day 1 should also be treated with the study drug after consultation with the Investigator at the next visit.

The primary efficacy endpoint is the percent change from baseline in the EASI total score at Day 29.

For the efficacy comparison of crisaborole versus vehicle, subjects from both Cohort 1 and Cohort 2 are included in the analysis, adjusted for cohort effect. For the efficacy comparison of crisaborole versus TCS, only subjects from Cohort 1 are included in the analysis. For the comparison of crisaborole versus TCI, only subjects from Cohort 2 are included in the analysis.

[figure not shown]
Safety and efficacy assessments will be conducted at the investigator site by a clinical assessor blinded for treatment arms.

A sub-study will be conducted at selected investigator sites to evaluate differences of changes in epidermal skin thickness as measured by Optical Coherence Tomography (OCT) between treatment groups in Cohort 1. (see Appendix 4).

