2.2. Study Design

This is a Phase 3b/4, multicenter, randomized, assessor blinded, vehicle and active (topical corticosteroid [TCS] and topical calcineurin inhibitor [TCI]) controlled study of the efficacy, safety and local tolerability of crisaborole ointment, 2% in pediatric and adult subjects, ages 2 years and older, with mild to moderate AD involving at least 5% treatable body surface area (%BSA). Treatment will be clinical assessor blinded for all treatment arms and double blinded for crisaborole ointment, 2% and vehicle treatment arms.

A total of approximately 600 subjects will be enrolled in the study, of which at least 150 subjects aged 2-6; at least 140 subjects aged 7-11; at least 120 subjects aged 12-17, and up to 90 subjects will be adults. Following the screening period (up to 35 days prior to Baseline/Day 1), eligible subjects will be randomized at the Baseline/Day 1 visit.

Randomization will be stratified by eligibility for TCS or TCI treatment as per national approved labels and eligibility provided in Section 4 of the protocol. Cohort 1 will be for subjects who are eligible for TCS therapy, and Cohort 2 will be for subjects who are not eligible for TCS therapy but eligible for TCI therapy. The investigational product will be applied BID for 28 days to the Treatable BSA identified at Baseline/Day 1. Any new AD on treatment eligible locations occurring following Baseline/Day 1 should also be treated with the study drug after consultation with the Investigator at the next visit.

The primary efficacy endpoint is the percent change from baseline in the EASI total score at Day 29.

For the efficacy comparison of crisaborole versus vehicle, subjects from both Cohort 1 and Cohort 2 are included in the analysis, adjusted for cohort effect. For the efficacy comparison of crisaborole versus TCS, only subjects from Cohort 1 are included in the analysis. For the comparison of crisaborole versus TCI, only subjects from Cohort 2 are included in the analysis.

[figure not shown]
Safety and efficacy assessments will be conducted at the investigator site by a clinical assessor blinded for treatment arms.

A sub-study will be conducted at selected investigator sites to evaluate differences of changes in epidermal skin thickness as measured by Optical Coherence Tomography (OCT) between treatment groups in Cohort 1. Detailed statistical analysis for sub-study will be given in a separate SAP.

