5.1. Hypotheses and Decision Rules

This study was terminated. The termination decision was made for business reasons only and was not related to any safety or efficacy concerns regarding crisaborole. Only 40% of planned participants were enrolled at termination. Due to small sample size, no hypotheses testing and decision rules. No statistical analysis and comparison will be performed. Only descriptive summary will be generated for safety data and some efficacy endpoints.

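### SAP 6.2.2 and 6.2.3 leave children under 12 with no itch-scale outcome, citing only low enrolment, although both scales remain listed secondary endpoints

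*SAP*

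**What the plan says.** SAP 6.2.2, on the scale for ages 6-11: "Due to the low enrollment, Patient Reported Itch Severity Scale will not be summarized". SAP 6.2.3, on the scale for children under 6: "Due to the low enrollment, Observer Reported Itch Severity Scale will not be summarized". Neither section gives a count or a threshold.

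The remaining itch summaries (SAP 6.2.1, 6.2.4 and 6.2.5) are restricted to subjects aged 12 and over. Protocol 9.2.3 requires each itch instrument to be analysed separately.

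SAP Table 2 and section 3.2.2 still list change from baseline on both under-12 scales as secondary endpoints. They also list 2- and 3-point improvement for children under 6.

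On planned numbers, SAP 2.2 sets minima of 150 for ages 2-6 and 140 for ages 7-11 out of about 600. For the older bands it has "at least 120 subjects aged 12-17, and up to 90 subjects will be adults". Protocol section 3 has the same quotas. On actual numbers, SAP 5.1 says only this: "Only 40% of planned participants were enrolled at termination". No age split is given.

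Other age-restricted outcomes are kept. For those aged 16 and over, SAP 6.2.6 reads "Descriptive statistics will be provided for observed change from baseline in DLQI for subjects". SAP 6.2.7 and 6.2.8 do the same for CDLQI (ages 4-15) and DFI (ages 2-17). SAP 6.4 splits EASI percent change by age group, race and geographic region, among other factors.

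**The concern.** The secondary objective on patient- and observer-reported outcomes covers everyone aged 2 and older, and Protocol 1.2 describes itching as the hallmark symptom of the disease. Two of the three instruments that measure it are left unreported, and those two cover the whole 2-11 age range.

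The stated reason does not separate what is dropped from what is kept. Low enrolment affected the whole trial, and the SAP's general response was to give up testing and describe the data. That response would serve these two scales as well. Children and caregivers were asked to score itch daily from Day 1 to Day 29. Without a table, a count or a note, a reader of the report cannot tell whether there were few data or simply no summary.

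**Working it through.** The documents give no sample size or precision target for itch, so no planned itch figure can be reproduced. The EASI power in Protocol 9.1 does reproduce: 12 / (34 × √(2/150)) − 1.96 = 3.06 − 1.96 = 1.10, or 86.4% against the stated 86%. It has no bearing on this point.

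**1. What is listed and what is summarized**

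| Outcome | Ages | Listed as secondary | Summarized |
|---|---|---|---|
| Peak Pruritus NRS | 12 and over | yes | yes (6.2.1, 6.2.4, 6.2.5) |
| Patient Reported Itch Severity Scale | 6-11 | yes | no (6.2.2) |
| Observer Reported Itch Severity Scale | under 6 | yes, with 2- and 3-point response | no (6.2.3; no responder section) |
| DLQI | 16 and over | yes | yes (6.2.6) |
| CDLQI | 4-15 | yes | yes (6.2.7) |
| DFI | 2-17 | yes | yes (6.2.8) |
| EASI percent change by age group | all | subset analysis | yes (6.4) |

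CDLQI does not fill the gap. It starts at age 4, its first question combines itch with soreness and pain, and only the change in CDLQI is summarized.

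**2. Planned share under 12** (quotas from SAP 2.2)

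- Minimum: (150 + 140) / 600 = 290 / 600 = 48.3%.
- Maximum: ages 12-17 at their minimum and no adults, (600 − 120) / 600 = 80%.
- The minima plus the adult cap sum to 150 + 140 + 120 + 90 = 500, so the ages of the other 100 are unspecified.

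**3. What that might mean at termination** (illustration only)

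Enrolled: 0.40 × 600 = 240. *Assumption:* the planned age mix was kept.

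- Under 12: 0.483 × 240 = 116, up to 0.80 × 240 = 192.
- With 1:1:2 allocation and equal cohorts, combined crisaborole, combined vehicle, TCS and TCI are each a quarter of the total: 116/4 = 29, up to 192/4 = 48.
- The scales cannot be pooled, and the quota bands (2-6, 7-11) do not match the scale bands (under 6, 6-11). *Further assumption:* both quotas sit at their minimum and ages are spread evenly within 2-6. Then under 6 is 0.40 × 150 × 4/5 = 48 (12 per group), and 6-11 is 0.40 × (140 + 150/5) = 68 (17 per group).
- If instead only 10% to 20% of those enrolled were under 12: 24 to 48 children, or 6 to 12 per group over both scales together.

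**4. Why none of these is a bound**

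The quotas are absolute targets for about 600. At 240 enrolled, up to 90 could be adults, and the other 240 − 90 = 150 could in principle all be aged 12-17, a band with no stated ceiling. The quotas therefore imply no minimum number under 12 at termination.

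**5. Does a small n prevent a summary?**

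SAP 5.2.2 specifies n, mean, SD, standard error, median, minimum and maximum. None is given a minimum sample size, and SAP 5.1 has already ruled out testing and comparison.

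**The case against.** The strongest defence is that the SAP, finalised after termination, says enrolment was low, and nothing in the documents contradicts that for these scales. The SAP version history records that Amendment 3 (August 2019) changed the pruritus scale descriptions, endpoints and analysis. The original protocol dates from March 2018, and Protocol section 4 has subjects screened before approval of Amendment 3 complete the version they consented to. Children with data on the current scales may therefore be a small, late subset, split further by scale and arm. This stands as a possibility, though the SAP does not give it as the reason. It is an argument for reporting n.

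Three stronger readings are tempting, and the documents do not support them:

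- *Data on more than 100 children are being set aside.* The 116 above rests on an assumed age mix and takes no account of the scale change.
- *Smaller groups were kept.* Scaling the adult cap gives 90/600 × 240 = 36, but the cap is an absolute 90 and DLQI also takes in ages 16-17. CDLQI and DFI each span wider age ranges than either dropped scale.
- *This is selective reporting driven by results.* SAP 5.1 attributes termination to business reasons and plans no comparison for any endpoint. The restriction to selected endpoints is logged in SAP Table 1 and repeated in section 6. The cuts are not confined to children: time to itch improvement has no analysis section for any age.

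The defence does not explain why description is acceptable for CDLQI, DFI and EASI by age group but not for these two scales. Nor does it explain why the endpoints stay listed without a note.

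**Conclusion.** The point holds as an unexplained gap in reporting. Both under-12 itch scales lose every outcome summary on a reason that applies to the whole trial, while remaining listed as secondary endpoints. The group affected was planned to be at least 48% of subjects; that figure comes straight from the quotas and needs no assumption. The number of children actually affected cannot be derived from the documents. It could be about 116 if the planned mix held, or far fewer. No test, comparison or primary result is touched, and no motive is shown. What is lost is the descriptive itch record for ages 2-11 and the reader's means of judging how sparse it was.

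**What to change.** Replace SAP 6.2.2 and 6.2.3 with the summary already used in 6.2.1, for each scale separately and unpooled: n, mean, SD, median and range of the weekly average change, by week, for the treatment groups in SAP 5.2. For the observer scale, add the listed 2- and 3-point responder counts. Show the eligible n, because SAP 4.1 limits threshold endpoints to participants whose baseline is at or above the threshold.

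If data on a scale prove too sparse to tabulate, report the number with data by scale and arm, provide a subject listing, and mark the endpoint in Table 2 and 3.2.2 as not summarized, with the reason.

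The cost is a few extra tables from data already collected. The estimates will be imprecise, and showing n makes that plain.

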6.4. Subset Analyses

Summary of percentage change from baseline in EASI will be summarized by treatment and by cohort, age group, sex, race, baseline ISGA, and geographic region.

6.5. Baseline and Other Summaries and Analyses

6.5.1. Baseline Summaries

Demographics and baseline characteristics including variables defined in [Section 3.4](#) will be summarized by treatment group according to Pfizer standards.

6.5.2. Study Conduct and Subject Disposition

Subjects evaluation, disposition, discontinuation will be summarized according to Pfizer standards.

6.5.3. Study Treatment Exposure

The exposure to study drug will be summarized by total number of applications, the total number of days of dosing, total amount of study drug used, and number and percentage of subjects who are compliant with the dosing regimen.

A subject will be considered compliant with the dosing regimen if he/she receives at least 45 but no more than 67 investigational product doses (ie, 80-120%, inclusive, of the expected number of doses) administered in accordance with the protocol.

6.5.4. Concomitant Medications and Non-drug Treatments

Prior drug and non-drug treatment, concomitant drug and non-drug treatment will be summarized according to Pfizer standards.

6.6. Safety Summaries and Analyses

Safety analysis will be based on the SAF.

Safety data will be presented in tabular and/or graphical format and summarized descriptively, where appropriate. All safety endpoints will be listed and summarized in accordance with Pfizer Standards. Categorical outcomes (eg, AEs) will be summarized by subject counts and percentage. Continuous outcome (eg, blood pressure, pulse rate, etc) will be summarized using N, mean, median, standard deviation, etc. Change from baseline in laboratory data, and vital signs will also be summarized. Subject listings will be produced for these safety endpoints accordingly. Cohort 1 and cohort 2 will be combined for crisaborole and vehicle arms for all safety summaries and analyses.

